## **Inclusion criteria:**

- Aged between 18 and 80 years.
- To provide informed consent in writing of voluntary participation in the study after having read the participant information sheet, and having consulted the doubts that may arise from it.
- Diagnosis of prediabetes or diabetes mellitus type 2 defined as: a) fasting glucose  $\geq 100$  mg/dL in the last 3 months; b) glycated hemoglobin  $\geq 5.7\%$  and  $\leq 6.5\%$ .

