### **Study visits:**

1. Prescreening visit: Inclusion and exclusion criteria assessment and blood collection if glucose or glycated hemoglobin is not available in previous 3 months. Healthy dietary and physical activity counselling is provided by a nutritionist; it should be maintained during all study. Baseline visit is scheduled in 2-4 weeks after lifestyle stabilization.

2. Baseline phase 1 visit: Clinical, biochemical, dietary, physical activity and anthropometric data are assessed. Computer-based randomization is performed. Alcohol-free beer (A or B according to randomization procedures) for the next 10 weeks is delivered to the participant who has to consume two per day. A nutritionist emphasizes healthy lifestyle counselling to the participant. A feces sample is collected if subjects accept to be included in microbiota sub study.
3. Intermediate phase 1 visit: Clinical, biochemical, dietary, physical activity and anthropometric data are assessed. Satiety after alcohol-free beer consumption is measured by a validated questionnaire. A nutritionist emphasizes healthy lifestyle counselling to the participant.
4. End of phase 1 visit: Clinical, biochemical, dietary, physical activity and anthropometric data are assessed. Satiety after alcohol-free beer consumption is measured by a validated questionnaire. A nutritionist emphasizes healthy lifestyle counselling to the participant. A wash-out period of 4-8 weeks is scheduled before the next phase start. A feces sample is collected if subjects accept to be included in microbiota sub study.
5. Baseline phase 2 visit: Clinical, biochemical, dietary, physical activity and anthropometric data are assessed. Alcohol-free beer (A or B: if subjects consumed alcohol-free beer A, he/she change to alcohol-free B and vice versa) for the next 10 weeks is delivered to the participant who has to consume two per day. A nutritionist emphasizes healthy lifestyle counselling to the participant. A feces sample is collected if subjects accept to be included in microbiota sub study.
6. Intermediate phase 2 visit: Clinical, biochemical, dietary, physical activity and anthropometric data are assessed. Satiety after alcohol-free beer consumption is measured by a validated questionnaire. A nutritionist emphasizes healthy lifestyle counselling to the participant.

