### **Statistical analysis plan**

The sample size was established by taking as main outcome variable the change of glucose concentration, whose clinical variability is estimated at 16 mg/dL in pre-diabetic population. This is the estimated value based on the epidemiological study carried out in Spanish population (PREDIMED) (Estruch R et al. N Engl J Med 2013;368:1279-90). It was expected to find a difference of 12 mg/dL in glucose levels between two intervention

arms. It was established a confidence level ( $1-\alpha$ ) of 95% (bilateral  $Z\alpha = 1,960$ ) and 90% of statistical power ( $1 - \beta$ ) (bilateral  $Z\beta = 1,282$ ), by obtaining a sample size of 37 subjects. It was estimated a 25% loss rate, so final sample was 44 subjects.

Different alcohol-free beers effects on study outcomes will be evaluated by repeated measures ANOVA or the Friedman test, as appropriate. When significant differences are detected, multiple comparisons will be made by using the Bonferroni correction for normally distributed variables or the Wilcoxon test for paired samples for variables with a skewed distribution. Treatment order will be entered in all models as an additional factor. Data will be presented as means ( $\pm$ SD) for continuous variables or medians and interquartile ranges (IR) for those with a skewed distribution). Statistical analysis will be processed using the software SPSS (version 24.0; SPSS, Chicago, Illinois, USA), using a significance level of  $P < 0,05$ .

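### The plan picks a parametric or rank test by whether a variable is normal or skewed and names no test for glucose; outcomes on the rank route lose the order adjustment and, in a two-beer comparison, power

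*Combined protocol and SAP*

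**What the plan says.** All of the analysis wording is in the Statistical analysis plan section of the combined document.

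- **First step.** Beer effects are assessed by "repeated measures ANOVA or the Friedman test, as appropriate". No criterion is given for what makes one or the other appropriate.
- **Second step.** Only if the first step is significant do pairwise comparisons follow, using the "Bonferroni correction for normally distributed variables or the Wilcoxon test for paired samples for variables with a skewed distribution".
- **Adjustment.** "Treatment order will be entered in all models as an additional factor".
- **Main outcome.** The sample size was set by "taking as main outcome variable the change of glucose concentration", with a variability of 16 mg/dL, an expected difference of 12 mg/dL, two-sided 5% significance and 90% power.

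The section names no normality test, threshold, transformation or time of decision. It does not mention residuals or within-person differences, and it does not say which route glucose will take. The Objective section lists glucose, HbA1c, insulin and HOMA together as the primary glycemic measures.

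**The concern.** Each participant drinks both beers, so the beer effect is estimated from within-person contrasts. A repeated measures ANOVA or paired t test needs those contrasts, or equivalently the model residuals, to be roughly normal. The shape of the variable across people is a different matter. A variable can be skewed between people and have well-behaved differences, or look normal and have heavy-tailed differences. A rule worded on the variable can therefore err in either direction.

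With no criterion and no named test for glucose, the choice in practice falls to whoever looks at the data. The plan does not say this outright, but no other basis for the choice is given.

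Three things are at stake for an outcome that goes down the rank route:

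1. The standard Friedman and Wilcoxon signed-rank tests take no covariate, so the order factor promised for every model cannot be fitted.
2. With two beers, the Friedman test uses only the sign of each person's difference, and it must be significant before Wilcoxon is used at all.
3. The rank tests as named give no adjusted estimate of the beer effect.

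Insulin and HOMA are the primary measures most likely to be called skewed. Triglycerides and C reactive protein are the likely ones among the secondary measures.

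**Working it through.** **1. The plan's own figure.** Inputs from the Statistical analysis plan: difference 12, SD 16, Z values 1.960 and 1.282.

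2 × (16 × (1.960 + 1.282) / 12)² = 2 × (16 × 3.242 / 12)² = 37.37, against the stated 37.

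This formula equals a paired calculation with an SD of differences of 16 × √2 = 22.6 mg/dL. A paired calculation with an SD of differences of 16 would give (16 × 3.242 / 12)² = 18.7. The plan does not state an SD of differences. I use 22.6 because it is the value at which 37 people give about 90% power, and I show 16 as the alternative.

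**2. Two-beer Friedman test at n = 37.** With two conditions the statistic is (2k − n)²/n, where k is the number of people whose difference favors one beer. It is compared with 3.841.

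- It rejects when |2k − 37| > √(3.841 × 37) = 11.9, that is k ≥ 25 or k ≤ 12.
- With normal differences, the chance that one person's difference is in the right direction is Φ(12 / 22.6) = Φ(0.530) = 0.702.
- The binomial probability of k ≥ 25 out of 37 at 0.702 is 0.71 (the lower tail is negligible).

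**3. Paired t test at n = 37.** The non-centrality is 0.530 × √37 = 3.23 on 36 degrees of freedom, with critical value 2.03. Power is 0.88.

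**4. The routes compared.** The table assumes normal differences, a mean difference of 12 mg/dL and an SD of differences of 22.6. The Wilcoxon and two-step columns are from simulation (4,000 trials per row).

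| n | Paired t | Wilcoxon alone | Friedman, two beers | Friedman, then Wilcoxon |
|---|---|---|---|---|
| 33 (44 less 25%) | 84% | 81% | 61% | 60% |
| 37 | 88% | 87% | 71% | 70% |
| 44 | 93% | 92% | 79% | 79% |

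Wilcoxon alone costs 1 to 3 points. Nearly all of the loss comes from the Friedman step before it.

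**5. Sensitivity to the SD.** If the SD of differences is 16, Φ(12/16) = 0.773. At n = 37, Friedman then has 94% power against 99% for the paired t test, a loss of about 5 points.

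**6. Order adjustment.** Let τ be the beer effect and π a shift between periods. The expected paired difference is τ − π in one order and τ + π in the other. With n₁ and n₂ completers in the two orders, the unadjusted mean difference is τ + π(n₂ − n₁)/(n₁ + n₂). With equal numbers the shift cancels in the mean but adds to the spread. With unequal numbers it biases the comparison. A model with an order or period term removes it. The Friedman and Wilcoxon tests named in the plan do not.

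**The case against.** **A stronger reading that a reader might infer.** Eligibility requires "fasting glucose $\geq 100$ mg/dL in the last 3 months". It is tempting to conclude that glucose is truncated and right-skewed by design, and so will be sent to a rank test although its within-person differences are normal. The documents do not support this, for five reasons.

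- The main outcome is named as a change. If normality is checked on the change, a cut on levels does not create the problem. The plan does not say which quantity is checked.
- The cut applies to a screening value up to 3 months old. Study visits then adds a stabilization period: "Baseline visit is scheduled in 2-4 weeks after lifestyle stabilization". Baseline and end-of-phase values are not themselves cut at 100 mg/dL.
- The Inclusion criteria do not say whether the glucose and HbA1c conditions must both be met. If either suffices, glucose is not cut in everyone.
- Nothing in the documents shows that the differences are normal. In the working above that is an assumption.
- The cut and the power loss do not occur together. Under assumed within-person SDs of 6 to 8 mg/dL the cut can make levels look non-normal more often, but the SD of differences is then 6√2 = 8.5 to 8√2 = 11.3, and all three tests have about 100% power for 12 mg/dL. At a within-person SD of 11.3 (SD of differences 16), levels failed a normality test while differences passed in 9–10% of simulated trials with the cut and 8–11% without it. At an SD of differences of 22.6 it likewise adds little or nothing.

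**Other points for the plan.** Choosing between parametric and rank methods by distribution is common practice, and the analyst may well intend to check changes or residuals. Wilcoxon by itself is nearly as powerful as the t test. The order in which the tests are chosen is not stated, so a choice made after seeing the data is an inference. The wording about multiple comparisons may also mean that the overall test covers several visits rather than two beers, in which case the Friedman figures above do not apply. A rank analysis can respect order by comparing period differences between the two sequence groups, but that is not one of the tests named.

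These points limit the size of the problem. They do not supply the missing rule, name a test for glucose, or let Friedman or Wilcoxon carry the order factor.

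**Conclusion.** The concern holds in a limited form. The plan selects the method on the distribution of the variable, fixes no test for the outcome that sizes the trial, and does not refer to the quantity on which the crossover comparison depends. Its rank route conflicts with its own commitment to enter treatment order in every model. These conclusions follow from the text and need no simulation.

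The power cost is conditional. It is about 17 points (88% to 71%), or 18 once Wilcoxon must also be significant. That assumes 37 completers, a two-beer Friedman test, normal differences, a difference of 12 mg/dL and an SD of differences of 22.6. It falls to about 5 points at an SD of differences of 16. The mg/dL figures describe glucose. For insulin, HOMA, triglycerides and C reactive protein, the documents give no variability from which to compute a loss, and their skewness is an expectation.

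No claim is made that eligibility pushes glucose onto the rank route. This should be corrected before the beer code is opened. It is not a flaw in the design itself.

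**What to change.** Replace the selection rule in the Statistical analysis plan with a named analysis, fixed before the beer code is opened:

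- One parametric beer comparison adjusted for order and period, for example a mixed model with beer, period and treatment order as fixed effects and participant as a random effect.
- Glucose and HbA1c on the original scale. Insulin, HOMA, triglycerides and C reactive protein on the log scale, with any change taken as a difference of logs.
- Fit judged on model residuals or within-person differences, never on the raw variable.
- Rank tests as sensitivity analyses only. They cannot replace the named analysis, and a two-beer Friedman test should not be a precondition for anything.
- A statement of whether glucose is analyzed as a change or as an end-of-phase level.

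The cost is a few lines of SAP wording, with no change to visits, data or sample size. The one small downside is that log-scale outcomes are reported as ratios between beers instead of differences in the original units.
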